# 13.3. Statistical Analyses of Pharmacokinetic Data

Statistical analyses of pharmacokinetic parameters will be responsibility of Oncology, Clinical Statistics, GSK. Statistical analysis of the exploratory compartmental PK parameters data will be the responsibility of CPMS, Quantitative Sciences, GSK.

PK data will be presented in graphical and/or tabular form and will be summarized descriptively.

For all statistical analyses, AUC( $0-\infty$ ), AUC(0-t), AUC( $0-\tau$ )), AUC(0-168), t1/2, and Cmax will be separately analysed after loge-transformation.

Individual plasma PK parameters values as well as descriptive summary (mean, SD, median, minimum, maximum, geometric mean, and the standard deviation, 95% confidence interval (CI) of log-transformed parameters (if applicable) by dose group will be reported.

Pre-dose trough concentration (C  $\tau$ ) samples obtained immediately before the morning dose on Days 8, 15, and 29 will be presented in a listing and will be summarized descriptively by dose.

Box plot figures will be generated based on dose normalized data for Cmax and AUC(0- $\infty$ ), AUC(0-168), and AUC(0- $\tau$ )) as a function of the dose administered.

Individual and Box Plot of Plasma GSK2636771 Pre-Dose Concentration Data on Day 8, 15 and 29 by Dose Cohort in Part 1 will be provided.

Statistical analysis of Cmax and AUC may be performed as appropriate dose proportionality.

# 13.4. Population Pharmacokinetic Analyses

Data permitting, population PK analysis will be performed by, or under the direct auspices of CPMS, GlaxoSmithKline.

Plasma concentration-time data from the groups in Part 2 may be combined with data from dose escalation and further analyzed using a population approach. A nonlinear mixed effect model may be used to determine population PK parameters and important covariates (biomarker, or disease related covariates).

PK data will be presented in graphical and/or tabular form and will be summarized descriptively.

# 14. PHARMACODYNAMIC AND BIOMARKERS ANALYSES

# 14.1. Pharmacodynamic Analyses

Pre-treatment and on-treatment biopsy tissues (tumor and normal skin) will be analyzed for markers of the HER3 pathway such as HER3 and including biomarkers indicative of pathway activation and proliferation (pHER3, Ki67) using IHC as the method to determine protein expression levels. Markers related to the other mechanisms of action attributed GSK2849330 such as ADCC and CDC may be analyzed.

Serum HER3 (also known as 'soluble HER3') pre and on-treatment analyses will be performed. Descriptive summary (mean, SD, median, minimum, maximum) of absolute test value will be reported by dose group. The summary of change from baseline serum HER3 will also be provided. The baseline of HER3 data is defined as the test value measured at Day 1 Pre-dose. The individual serum HER3 concentration over time data for will be plotted. Box plot figures will be generated as a function of the dose administered. Listing of the serum HER3 data will be provided.

Data permitting, exploratory population PD analyses of other peripheral blood markers will be provided.

# 14.2. Biomarker Analyses

The results of these biomarker investigations which include analysis of biomarker associated with anti-cancer activity parameters may be reported separately from the main CSR. All endpoints of interest from all comparisons will be descriptively and/or graphically summarized as appropriate to the data.

Descriptive summary (mean, SD, median, minimum, maximum) for CD marker data will be reported by dose group. A listing of CD marker data will be provided.

Additional exploratory analyses may be performed to further characterize novel biomarkers.

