7.6.3. Blood Samples

Blood-based markers have the important advantage that specimens are readily available, simple to prepare and store, and can be taken prior to and during treatment. This allows for the assessment of predictive markers based on the baseline evaluation as well as markers of activity and resistance based on changes that occur during treatment.

Blood samples will be collected for analysis of potential surrogate markers of GSK2849330 activity. These analyses may include, but are not limited to measurement of specific blood proteins and cell populations (e.g., PBMCs: CD16, CD56, CD69, CD107, CD19, CD8, CD4, CD3, CD14), complement activity (e.g., CH50), inflammatory cytokines (e.g., IFN γ , TNF α , IL-2, IL-6), growth factors, soluble HER3, or mutations in circulating free tumor DNA (Refer to Section 7.6.3.1).

Blood samples drawn for investigating both predictive and PD biomarkers will be by study part and subject cohort or group:

Details on sample collection, processing, storage and shipping procedures are provided in the SPM.

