13.5.2. Other Comparisons of Interest

In Part 1, PK parameters including, but not limited to, AUC(0-t), AUC(0-τ), AUC(0-∞), C_{max}, t_{max}, and MRT of GSK2849330 will be descriptively compared between dose

levels in tabular or graphic formats. In Part 2, other safety, PK and clinical activity data than the primary endpoints will also be evaluated and compared between different treatment groups.

- PK: PK parameters including, but not limited to, AUC(0-t), AUC(0- τ), AUC(0- ∞), Cmax, tmax, and MRT of GSK2849330 will be descriptively compared between dose levels in tabular or graphic formats.
- PD biomarker: Changes from baseline in PD markers, the markers of inflammatory response activation from blood and markers in skin and tumor biopsies will be evaluated and summarized for each dose cohort or group.
- Clinical anti-cancer activity: The number of CRs, PRs, stable diseases (SDs) and PDs for each dose cohort or group will be listed using RECIST, irRC, and mRECIST and summarized if appropriate.

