#### 9.2.7. Change from baseline

Change from baseline will be presented for safety data as described in Section 19.

Change from baseline is calculated as:

• For records occurring after baseline: (visit value) – baseline value.

Percent change from baseline is calculated as:

• For records occurring after baseline: ((change from baseline) / baseline value) \* 100

If either the baseline or visit value is missing, the change from baseline and/or percent change from baseline is set to missing as well.

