## Tables

No.	Population	IDSL / TST ID / Example Shell	Title	Programming Notes	Deliverable [Priority]
12.1	PD	PD1/Shell	Summary of Serum HER3 Data by Dose Cohort		SAC
12.2	PD	PD1/Shell	Summary of Change from Baseline of Serum HER3 Data by Dose Cohort		
12.3	PD	PD1/Shell	Summary of CD marker Data (%) by Dose Cohort		SAC
12.4	PD	PD1/Shell	Summary of CD marker Data (cells/cumm) by Dose Cohort		SAC
12.5	PD	Non-standard	Listing of Biomarker Data	by subjid, visit, bicat, bimeth, biorres in BIOMARK dataset	SAC
12.6	PD	PD10/Shell	Listing of Serum HER3 Data		SAC
12.7	PD	PD10/Shell	Listing of CD Marker Data		SAC

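### The SAP summarises circulating CD markers only as raw values by time, although the protocol commits to change from baseline in PD markers

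*SAP*

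**What the plan says.** Protocol 13.5.2 lists the PD summaries: "Changes from baseline in PD markers, the markers of inflammatory response activation from blood and markers in skin and tumor biopsies will be evaluated", and these are to be summarised for each dose cohort or group. Protocol 7.6.3 names the blood cell populations of interest ("PBMCs: CD16, CD56, CD69, CD107, CD19, CD8, CD4, CD3, CD14") as possible surrogates for drug activity. Circulating cells before and after treatment are an exploratory endpoint in both parts.

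The SAP treats two kinds of blood marker differently.

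- **Serum HER3 (SAP 14.1).** Absolute values are summarised, baseline is defined as Day 1 pre-dose, and "The summary of change from baseline serum HER3 will also be provided". The display list carries this through as Table 12.2, "Summary of Change from Baseline of Serum HER3 Data by Dose Cohort".
- **CD markers (SAP 14.2).** "Descriptive summary (mean, SD, median, minimum, maximum) for CD marker data will be reported by dose group", plus a listing. The display list in SAP 19.1.4 has Table 12.3, "Summary of CD marker Data (%) by Dose Cohort", and Table 12.4, "Summary of CD marker Data (cells/cumm) by Dose Cohort". The example shell shows n, mean, SD, median, minimum and maximum by treatment and planned time, with a pre-dose row and no change column. No CD figure is planned.

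The SAP's general rule does not fill the gap, because SAP 9.2.7 says "Change from baseline will be presented for safety data as described in Section 19".

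**The concern.** For a marker of drug activity the quantity of interest is what happens within a subject after dosing. The protocol says so and the SAP's CD displays do not give it. Protocol 13.7 also asks that departures from its analysis plan be documented in the analysis plan and the study report. The SAP explains its shortened efficacy analysis by the early stopping of the study, but says nothing about leaving out change from baseline for the CD markers.

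A reader of Tables 12.3 and 12.4 would have to subtract one row mean from another. In very small groups that subtraction has two weaknesses. Its spread cannot be obtained from the table, so the precision of the within-subject comparison is lost. And if the two rows do not contain the same subjects, the difference can show a change that occurred in nobody, or hide one that did occur.

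**Working it through.** No sample size, power or alpha figure in the plan bears on this point, so there is no stated figure to reproduce. The check is a comparison of the texts, followed by illustrations under stated assumptions.

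**1. Commitment against delivery.**

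| Item | Serum HER3 | CD markers |
|---|---|---|
| Change from baseline promised (Protocol 13.5.2) | yes, as a PD marker | yes, as PD markers |
| Raw summary in the SAP | Table 12.1 | Tables 12.3, 12.4 |
| Change-from-baseline summary in the SAP | Table 12.2 | none |
| Baseline defined for the marker | Day 1 pre-dose | not stated |

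**2. Group sizes.** Protocol Table 3 and section 13.2.1 plan 1 escalation subject at 1.4 mg/kg and 3 in each later cohort (1 + 4 × 3 = 13, which agrees with the stated minimum), plus up to 3 PK/PD subjects per cohort. SAP 7.1 pools escalation and PK/PD subjects in treatment codes 3, 4 and 5. Part 1 groups are therefore planned at about 1 to 6 subjects.

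**3. Rows that need not hold the same subjects.**
- Protocol Tables 9 and 10 (PK/PD cohorts), footnote 14, schedule a 24-hour blood-marker sample. Tables 7 and 8 (escalation cohorts), footnote 14, do not.
- The 6-hour sample is optional when the infusion lasts 3 hours or longer, and the progression sample exists only for subjects who progress.
- The PD Population in SAP 6 needs at least one pre-treatment and on-treatment pair, not a pair at every time. Missing data are not imputed (Protocol 13.4.4).

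Take a pooled group with a escalation and b PK/PD subjects, and let no subject change. The pre-dose mean uses all a + b subjects and the 24-hour mean uses only the b. The apparent shift is

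mean_b − (a·mean_a + b·mean_b)/(a + b) = [a/(a + b)] × (mean_b − mean_a).

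With a = b = 3 it is half the difference between the two subset means. If both subsets are random draws with between-subject SD σ, this shift has SD ½ × σ × sqrt(2/3) = 0.408σ. At an assumed coefficient of variation (CV) of 30%, 50% or 80%, that is 12%, 20% or 33% of the marker mean. The within-subject change is zero throughout. The documents do not say which scheduled blood samples were assayed for CD markers, so the 24-hour case is conditional on that.

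**4. Missed samples or drop-out, if any.** Simulated lognormal values with CV 30% to 80%, no subject changing and one subject lost at random: the raw mean moves by more than 10% in 40% to 73% of cohorts of 3, and in 6% to 41% of cohorts of 6. A hand example: values of 100, 200 and 600 average 300; without the third subject the mean is 150, a fall of 50% with zero within-subject change. That example was chosen to be extreme.

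**5. Precision when the subjects are the same.** With SD s at each time and within-subject correlation r (assumed; not in the documents), treating the two rows as independent gives a standard error of s·sqrt(2/n). The within-subject change has s·sqrt(2(1 − r)/n). The ratio is 1/sqrt(1 − r): 1.0 at r = 0, 1.2 at 0.3, 1.4 at 0.5, 1.8 at 0.7 and 3.2 at 0.9. For n = 6 and CV 50%, that is 29% of the mean unpaired, against 20% (r = 0.5) or 16% (r = 0.7) paired.

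**The case against.** The case on the other side is substantial.

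- **Purpose.** SAP 7 plans no formal comparisons and describes most analyses as descriptive or exploratory. No standard error, interval or test is planned for CD markers, so the ratios in step 5 describe a comparison that the SAP does not formally make. This stands and limits the severity.
- **Drop-out.** A reader might infer that subjects are known to leave before Day 29. The documents do not show this. Scheduled sampling for these markers ends at Day 29 (Day 43 on the three-weekly schedule) apart from progression, the first on-treatment disease assessment comes at week 8 or 9, and escalation subjects who stop early for reasons other than toxicity may be replaced. The shell also prints n at each time, so a loss would be visible. Step 4 is therefore conditional.
- **Other routes.** SAP 14.1, 14.2 and 16 allow further exploratory analyses of blood markers, Table 12.7 lists CD data by subject, and biomarker results may be reported outside the main study report. In groups this small a reader can work out each change from the listing. But these routes are optional or unsummarised, and none pre-specifies the summary that Protocol 13.5.2 commits to.
- **Reading from the pre-dose row.** A mean shift can be read off Tables 12.3 and 12.4. Its spread cannot, and nothing ensures that the rows hold the same subjects.

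**Conclusion.** The mismatch between protocol and SAP holds on the text. Change from baseline in PD markers is committed to, it is delivered for serum HER3 and not for the CD markers, and the departure is not recorded. The consequence is lost precision and, where sampled subjects differ between rows, a row difference that can mislead. How large either would be depends on an unknown correlation, spread and pattern of samples; the figures in the working are illustrations.

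Two stronger readings are tempting and are not supported. One is that between-subject spread confounds the before-and-after comparison. It does not: spread costs precision, and only a changing set of subjects can bias the difference. The other is that these tables are the study's cell read-out of antibody-dependent cytotoxicity. That is an inference from markers such as CD16 and CD56. Protocol 7.6.3 presents the blood markers only as possible surrogates for drug activity, and the cytotoxicity markers named in Protocol 7.6.1.2 are perforin and granzyme B in tumour biopsies.

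Severity is minor: the endpoint is exploratory, the summary is descriptive, and no decision rule depends on it.

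**What to change.** In SAP 14.2 and 19.1.4, add two tables of change from Day 1 pre-dose for the CD markers, one in percent and one in cells/cumm, using the Table 12.2 shell. State the baseline for these markers, and count at each time only subjects with both values. Keep Tables 12.3 and 12.4 as support. Showing counts as a ratio to baseline is optional. If the tables are not wanted, record the departure from Protocol 13.5.2 and the reason, as Protocol 13.7 asks. The cost is a sentence or two of SAP text and two tables from a shell that already exists, with no new data.

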# 15. IMMUNOGENICITY ANALYSIS

Serum samples for determination of anti-GSK2849330 antibodies will be taken from all subjects in this study at the time-points specified in the Time and Events Tables in Section 7.1 in the protocol. Samples will be analyzed for the presence of anti-GSK2849330 antibodies using a validated immunoelectrochemiluminescent (ECL) assay. The assay involves screening, confirmation and titration steps (tiered-testing approach). If serum samples contain anti-GSK2849330 antibodies, they will be further analyzed for the specificity of antibodies by a confirmation assay. Confirmed positive samples will be titrated to obtain the titers of antibodies.

Immunogenicity results will be summarized and the results for antibody positive subjects will be presented in a listing. The immunogenicity results of anti-GSK2949330 positive incidence and titer will be reported at the end of the study.

# 16. PHARMACOKINETIC/PHARMACODYNAMIC ANALYSES

If data permit, exploratory PK/PD analyses may be performed by, or under the direct auspices of, CPMS, GlaxoSmithKline to examine the potential relationships between GSK2949330 PK and PD endpoints such as total and phosphor-HER3 from tumor tissue, pre- and post-treatment biomarkers (cells, proteins, ribonucleic acid [RNA] and/or deoxyribonucleic acid [DNA]) from circulation, skin, and/or tumor tissue. In addition, analyses may be may be performed to examine the potential relationship between GSK2949330 concentration/PK and clinical activity endpoints such as ORR and/or safety measurements such as QTc or AEs. The data from this study may be combined with data from other studies for a population PK/PD analysis, which will be reported separately. Further details of population PK/PD analyses will be described in a separate RAP.

# 17. PHARMACOGENETIC DATA ANALYSES

Specific sections of DNA may be selected from areas of the genome (e.g., candidate genes) known to encode the drug target, drug metabolizing enzymes, areas associated with mechanisms underlying AEs, and those linked to study disease and, thus, linked to drug response.

The candidate genes that may be investigated in this study include the following: the GSK Absorption, Distribution, Metabolism and Excretion genes. These play a central role in drug PK and PD. In addition, continuing research may identify other enzymes, transporters, proteins, or receptors that may be involved in response to GSK2849330. The genes that may code for these proteins may also be studied.

Genome-wide scans involving a large number of polymorphic markers (e.g., single nucleotide polymorphisms) located throughout the genome. This approach is often employed when potential genetic effects are not well understood.

The results of PGx investigations will be reported either as part of the main clinical study report or as a separate report. All endpoints of interest from all comparisons will be descriptively and/or graphically summarized as appropriate to the data. In all cases, appropriate statistical methods will be used to analyze the genetic markers in the context of other clinical data. Statistical methods may include, but are not limited to Hardy-Weinberg Equilibrium testing, Comparison of Demographic and Baseline Characteristics by Genotype, Evaluation of Genotypic Effects, Evaluation of Treatment by Genotype and Gene-Gene Interaction, Linkage Disequilibrium, Multiple Comparison and Multiplicity and/or Power and Sample Size Considerations. Detailed description of the analyses to be conducted will be documented in the PGx RAP.

## 19. ATTACHMENTS

### **19.1.** Table of Contents for Data Display Specifications

For the Clinical Study Report the following section numbering will apply:

Section 9: Study Population

Section 10: Efficacy

Section 11: Safety presented

Section 12: Pharmacokinetic

Section 13: Pharmacodynamic / Biomarker

Section 14: Immunogenicity

Listed below are the planned figures, tables and listings to be produced for inclusion in the GSK2849330 clinical study report:

- The 'IDSL No. / Example Shell' column refers to the relevant example in the Integrated Data Standards Library (IDSL) database
- Unless otherwise indicated, these refer to the core IDSL data standards located under:
  - $\circ$  'Data Standards'  $\rightarrow$  'By Component' in the IDSL database
- 'CP' refers to the Clinical Pharmacology (CP) modified core IDSL standards located under:
  - $\circ$  'Supporting Documentation'  $\rightarrow$ 'TST Use of IDSL Core Choices'  $\rightarrow$  'Clin Pharm' in the IDSL database
- 'PD' refers to the Clinical Pharmacology data standards located under 'Data Standards' → 'By Therapeutic Component' → 'Clin Pharm' in the IDSL database.

# 19.1.1. Study Population

### **Tables**

No.	Population	IDSL No. / Example Shell	Title	Additional Programming Notes	Deliverable
9.1	All Treated	ES6	Summary of Study Eligibility in Screening	Including screening failure and reason of failure	SAC
9.2	All Treated	POP1	Summary of Analysis Populations	Footnote subject ID and excluded population	SAC
9.3	All Treated	DV1A	Summary of Protocol Deviation	Add a column for Total	SAC
9.4	All treated	ES1	Summary of Subject Disposition		SAC
9.5	All treated	DM1	Summary of Demographic Characteristics	Include height, weight and BMI at screening or baseline, and country; add age by categories.	SAC
9.6	All treated	DM5	Summary of Race		SAC
9.7	All treated	LA1	Summary of Disease Characteristics at Baseline		SAC
9.8	All Treated	CM8	Summary of Concomitant Medication by Ingredient for Medication Started prior Study Treatment	only for medications start prior to study and continue during study	SAC
9.9	All Treated	CM8	Summary of Concomitant Medication by Ingredient	Including medications start on or after date of first dose; excluding ones taken post therapy period.	SAC
9.10	All Treated	AC3	Summary of Prior Anti-Cancer Therapies	/arenv/arprod/gsk2636771/p3b115717/sac /drivers/t_ac3.sas	SAC
9.11	All Treated		Summary of Baseline ECOG Performance Status	/arenv/arprod/gsk2636771/p3b115717/sac /drivers/t_ecog.sas	SAC
9.12	All Treated	PS4A/ Shell	Summary of Change from Baseline in ECOG Performance Status		SAC

### HER117158

No.	Population	IDSL No. / Example Shell	Title	Additional Programming Notes	Deliverable
9.1	All Treated	ES6	Summary of Study Eligibility in Screening	Including screening failure and reason of failure	SAC
9.13	All Treated		Summary of Country and Age Group	arenv/arprod/gsk2636771/p3b115717/sac/ drivers/t_dm_agecat.sas	
9.14	All Treated		Summary of Baseline HER3 and NRG1 Status		

# 19.1.2. Efficacy Figures and Tables

# Tables

No.	Population	IDSL / TST ID / Example Shell	Title	Programming Notes	Deliverable
10.1	All Treated	RE1a	Summary of Investigator Assessed Best Response (RECIST 1.1 Criteria)	Best Resp. only	SAC
10.2	All Treated	RE5	Listing of Investigator-Assessed Tumor Responses (RECIST1.1 Criteria)		SAC
10.3	All Treated	LA2	Listing of Target Lesion (RECIST v1.1)		SAC
10.4	All Treated	LA3	Listing of Non-target Lesion (RECIST v1.1)		SAC

# 19.1.3. Safety Figures & Tables

# Figures

No.	Population	IDSL No. / Example Shell	Title	Programming Notes	Deliverable
11.1	All Treated	OEX12	Plot of Duration of Treatment (Weeks) by Primary Tumour Type and Initial Dose	/arenv/arprod/gsk2636771/p3b 115717/sac/drivers/f_durtrt.sas	SAC
11.2	All Treated	OECG4	QTcF Shifts from Baseline to Worst-case Post Baseline		SAC

## Tables

No.	Population	IDSL No. / Example Shell	Title	Programming Notes	Deliverable
11.1	All Treated	OEX1	Summary of Exposure to GSK2849330	Including Ave. Dose, Cum. Dose, Time on study treatment (weeks)	SAC
11.2	All Treated	OEX3a	Listing of Exposure to GSK2849330		SAC
11.3	All Treated	IP2	Listing of Investigational Product Compliance	If IPCOMP data is available	SAC
11.4	All Treated		Summary of Dose Reduction	arenv/arprod/gsk2636771/p3b1157 17/sac/drivers/t_dosredgsk.sas	SAC
11.5	All Treated		Summary of Dose Interruption	arenv/arprod/gsk2636771/p3b1157 17/sac/drivers/t_dosintgsk.sas	SAC
11.6	All Treated	AE3	Summary of All Adverse Events by Frequency		SAC
11.7	All Treated	OAE07	Summary of All Adverse Events by Maximum Grade		SAC
11.8	All Treated	AE3	Summary of Drug-Related Adverse Events		SAC

No.	Population	IDSL No. / Example Shell	Title	Programming Notes	Deliverable
11.9	All Treated	OAE07	Summary of Drug-Related Adverse by Maximum Grade		SAC
11.10	All treated	AE3	Summary of Serious adverse events by Frequency		SAC
11.11	All treated	OAE07	Summary of Serious adverse events by Maximum Grade		SAC
11.12	All treated		Adverse Events Overview	arenv/arprod/gsk2636771/p3b 115717/sac/drivers/t_ae_overv iew.sas	SAC
11.13		AE8	Listing of Fatal Serious Adverse Events		SAC
11.14	All treated	DL3	Listing of Dose-Limiting Toxicities	For DE cohorts only	SAC
11.15	All treated	AE8	Listing of subjects with Grade 3 or Higher Adverse Events		SAC
11.16	All treated	AE3	Summary of Adverse Events of Special Interest	See Section 12.3	SAC
11.17	All treated	AE8	Listing of Cardiovascular Adverse Events	See RAP Section 12.4	SAC
11.18	All treated	AE8	Listing of AEs leading to dose delay or reduction or interruption		SAC
11.19	All treated	AE8	Listing of Adverse Events Leading to Permanent Discontinuation of Study Treatment or Withdrawal from the Study		SAC
11.20	All treated	DTH3	Listing of deaths	including time from last dose	SAC
11.21	All treated		Summary of Non-serious Adverse Events by Preferred Team with Occurrences >=5%	/arenv/arprod/gsk2636771/p3 b115717/sac/drivers/t_ae_non _ser.sas	SAC
11.22	All treated		Summary of Serious Adverse Events by Preferred Term Including Drug-related Status and Fatal Status	/arenv/arprod/gsk2636771/p3 b115717/sac/drivers/t_ae_ser_ 2.sas	SAC
11.23	All treated	OLB6	Summary of Clinical Chemistry Toxicity Grade Change from Baseline		SAC

No.	Population	IDSL No. / Example Shell	Title	Programming Notes	Deliverable
11.24	All treated	OLB6	Summary of Haematologic Toxicity Grade Change from Baseline		SAC
11.25	All treated	OLB6	Summary of Urinalysis Toxicity Grade Change from Baseline		SAC
11.26	All treated	OLB11B	Summary of Clinical Chemistry Data Changes from Baseline with Respect to the Normal Range		SAC
11.27	All treated	OLB11B	Summary of Haematologic Data Changes from Baseline with Respect to the Normal Range		SAC
11.28	All treated	OLB11B	Summary of Urinalysis Data Changes from Baseline with Respect to the Normal Range		SAC
11.29	All treated	UR3	Summary of Urinalysis Dipstick Results		SAC
11.30	All treated	OLIVER1	Summary of Hepatobiliary Laboratory Abnormalities		SAC
11.31	All treated	OLB7	Listing of Liver Function Tests for Subjects Meeting Potential Hy's Law	put 'No data to report', if no subject meets the Law,	SAC
11.32	All treated	OVT1A	Summary of Heart Rate and Temperature Worst-Case Change from Baseline		SAC
11.33	All treated		Summary of Blood Pressure Worst-Case Change from Baseline	arenv/arprod/gsk2636771/p3b 115717/sac/drivers/t_vit_chgbl _bp.sas	SAC
11.34	All treated		Summary of Worst-Case Increases in QTcF	arenv/arprod/gsk2636771/p3b 115717/sac/drivers/t_qtcf4.sas	SAC
11.35	All treated		Summary of Worst-Case QTcF Increases from Baseline	arenv/arprod/gsk2636771/p3b 115717/sac/drivers/t_qtcf3.sas	SAC
11.36	All treated	EG3	Listing of Subjects with QTcF >=501 msec		SAC
11.37	All treated	EG2	Summary of ECG Values		SAC

No.	Population	IDSL No. / Example Shell	Title	Programming Notes	Deliverable
11.38	All treated	EG1	Summary of ECG Findings	arenv/arprod/gsk2636771/p3b 115717/sac/drivers/t_ecgfind.s as	SAC
11.39	All treated	OLVEF1B	Summary of Left Ventricular Ejection Fraction Change from Baseline		SAC
11.40	All treated		Summary of Worst-Case ECOG Performance Status Shifts from Baseline	arenv/arprod/gsk2636771/p3b 115717/sac/drivers/t_ecog_shi ft.sas	SAC

